## Knee Extensors

The knee extensors (quadriceps) are widely recognized to be spared in GNE Myopathy relative to other lower extremity muscle groups making it a defining feature of the disease and instrumental in making a differential diagnosis. Dynamometry data from the Phase 2 study showed significant weakness in this muscle group relative to normative data although the magnitude of the weakness was considerably less than in the other lower extremity muscle groups tested. Biopsy data from the Phase 2 study revealed limited pathology suggesting that there was considerable viable muscle tissue remaining in this group. For this reason, strength in the knee extensors, as measured by dynamometry, is included as an endpoint to assess the effect of SA-ER on a relative intact lower extremity muscle group. It should be noted, however, that there can be considerable variability in dynamometry results for this large, intact muscle group, particularly among stronger patients who can overpower the strength of the test administrator during the maneuver.

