### 4.2 Key Secondary Clinical Efficacy Endpoints

- Lower Extremity Composite Score: Muscle strength based on MVIC against a dynamometer will be measured bilaterally in the following lower extremity muscle groups: knee flexors, hip flexors, hip extensors, hip abductors and hip adductors. The LEC is derived from the sum of the average of the right and left total force values (measured in kg).
- Muscle strength in knee extensors: bilateral total force defined as the average of the right and left force values (measured in kg).
- GNEM Functional Activities Scale Mobility: Lower extremity use and function will be assessed using the Mobility domain of the GNEM-FAS instrument a disease-specific measure developed to assess the functional impact of changes in muscle strength on mobility (reflective of the lower extremities).

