## 10.2 Missing Observation in Hand Held Dynamometry and GNEM-FAS

Imputation rules outlined in this section for dynamometry are defined below and are based on the distinct pattern of muscle weakness associated with GNE Myopathy and the features of the dynamometers used in this study. The most common cause of missing data is muscle weakness severe enough to prevent the subject from registering the minimum amount of force against the dynamometer required to obtain a measurement during a maximum voluntary isometric contraction maneuver. In those cases, the value is imputed to 0, and preserves the ability to calculate the UEC and LEC scores. There are some scenarios in which non-random missing HHD data values result in missing UEC and LEC values. When strength in a particular muscle group exceeds the resistance that can be applied by the administrator, a reliable value cannot be obtained from the dynamometer. This is a recognized limitation of a hand-held device (Visser et al. 2003). In GNE Myopathy, the only muscle group at risk for this scenario is the knee extensors, due to the relative sparing of the quadriceps. All other non-random missing HHD data are related to the clinical condition of the subject at the time of the testing where a test may not be administered due to pain, injury, contracture or another extenuating circumstance that could cause discomfort to the subject. The proposed plan for the handling of this data is intended to provide the most accurate estimate of muscle strength and physical function possible based on knowledge of the disease and the outcome measures obtained during the conduct of previous studies.

Missing observations in HHD for individual muscle group will be imputed based on reason for missing and if the muscle strength measurement is missing on both sides or one side. The table below provides a summary of the imputation rule followed by detailed descriptions.

Instrument	Missing Reason	Imputation
HHD missing BOTH sides	Too Weak	0
	Too Strong	NA , UE/LE composite not computed
	Pain	NA , UE/LE composite not computed
	Injury	NA , UE/LE composite not computed
	Contracture	NA , UE/LE composite not computed
	Other	NA , UE/LE composite not computed
HHD missing ONE side	Too Weak	0
	All other reasons	The value from the other side that was measured

*Missing Reason = Weakness*

A value of 0 should be imputed for a W.

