- If both sides are W, a value of 0 is assigned to each side and the muscle group IS counted as part of the UE or LE composite.
- If one side is W, a value of 0 is assigned to that side and the 0 is averaged with the value from the other side. The muscle group IS counted as part of the UE or LE composite.

*Missing Reason = Contracture*

A value of 0 should NOT be imputed for a C. A C is missing data because the test was not performed due to the contracture.

- If both sides are C (which would be rare), then the data for this muscle group is missing and the UE or LE composite will be set to missing.
- If one side is C, then the data is missing from this side and the value from the other side should be used to reflect the total strength for this muscle group. The muscle group IS counted as part of the UE or LE composite.

*Missing Reason = Pain*

A value of 0 should NOT be imputed for a P. A P is missing data because the test was not performed due to pain.

- If both sides are P, then the data for this muscle group is missing and the UE or LE composite will be set to missing.
- If one side is P, then the data is missing from this side and the value from the other side should be used to reflect the total strength for this muscle group. The muscle group IS counted as part of the UE or LE composite.

*Missing Reason = Injury*

A value of 0 should NOT be imputed for an I. An I is missing data because the test was not performed due to pain.

- If both sides are I, then the data for this muscle group is missing and the UE or LE composite will be set to missing.
- If one side is I, then the data is missing from this side and the value from the other side should be used to reflect the total strength for this muscle group. The muscle group IS counted as part of the UE or LE composite.

*Missing Reason = Too Strong*

An S indicates that the test was attempted but that the subject overpowered the administrator and a valid value could not be obtained.

- If both sides are S, then the data for this muscle group is missing and the UE or LE composite will be set to missing.
- If one side is S, then the data is missing from this side and the value from the other side should be used to reflect the total strength for this muscle group. The muscle group IS counted as part of the UE or LE composite.

*Missing Reason = OTHER*

No value should be imputed if there is an O.

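### Knee-extensor tests coded 'too strong' are handled as ordinary missing data, so gains on a key secondary endpoint can be deleted, understated or recorded as losses

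*SAP*

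**What the plan says.** SAP Section 10.2 scores a missing dynamometry value by its reason. For the too-strong code it states: "An S indicates that the test was attempted but that the subject overpowered the administrator and a valid value could not be obtained". It adds that in this disease "the only muscle group at risk for this scenario is the knee extensors". SAP Section 3.3 (Knee Extensors) warns of variable results, "particularly among stronger patients who can overpower the strength of the test administrator during the maneuver". After describing the too-strong case, Section 10.2 turns to the remaining reasons with the words "All other non-random missing HHD data are related to the clinical condition of the subject", so it classes S as non-random too.

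The scoring rule has two parts:

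- Both sides S: "If both sides are S, then the data for this muscle group is missing".
- One side S: "If one side is S, then the data is missing from this side and the value from the other side should be used" for the whole muscle group. SAP Sections 5.3 and 7.1 give the same fill-in for any one-sided missing value, apart from weakness in 7.1.

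A test that fails because the muscle is too weak is scored 0.

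Knee-extensor force, the mean of right and left in kg, is one of the three key secondary endpoints under Hochberg (SAP 4.2, 8.8.1). SAP 8.1 leaves randomly missing values missing in the GEE. Its sensitivity analysis removes only the dropout imputation. The per-protocol repeat is defined by compliance (SAP 6.2). Neither changes how S is scored.

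**The concern.** An S is not an unknown value. It says the force was above what that tester could resist, which makes it right-censored. The SAP uses the equivalent information at the bottom of the scale (too weak counts as 0) but discards it at the top.

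The chance of an S rises with strength, which is what the endpoint measures. If SA-ER preserves or improves strength, more SA-ER than placebo values should become S. Deleting them, or replacing them with the side the tester could still hold, removes part of the effect the endpoint is meant to show. A disappointing knee-extensor result could then not be told apart from a scoring artefact, and a repair chosen after unblinding would carry less weight.

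**Working it through.** **Inputs.** The scoring formula is (left + right)/2 (SAP 5.3, 10.3), with the S rules above. The documents state no figure for this issue, so there is none to reproduce: no frequency of S, tester limit, or knee-extensor SD, effect or power.

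**Step 1: one-sided S at follow-up.** Let the weaker side be L at baseline and the stronger side L + d. The baseline score is L + d/2. Both sides gain g and the stronger side becomes S, so the follow-up score is L + g. The recorded change is (L + g) − (L + d/2) = g − d/2. It is negative when d > 2g.

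| Baseline R/L (kg) | True gain, both sides | d/2 | Recorded change |
|---|---|---|---|
| 40/38 | +2 | 1 | +1.0 |
| 40/34 | +2 | 3 | −1.0 |
| 40/30 | +3 | 5 | −2.0 |
| 40/34 | 0 | 3 | −3.0 |

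**Step 2: S at baseline.** If both sides are S there is no baseline, so the subject has no change score on this endpoint. With one side S, the error reverses. Take true values 40/34 with the right side S, so the recorded baseline is 34. If both sides then fall by 2 and become measurable, the score is (38 + 32)/2 = 35: a recorded +1.0 for a true −2.0.

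**Step 3: knock-on to dropout imputation.** SAP 7.1 projects a decline for early withdrawals whose last change is negative, and it names the knee extensors. The 40/34 subject above, with a true gain of 2 kg but a recorded −1.0, would qualify. If that was the only visit, at Week 8, the projected Week 48 value would be −1.0 × 48/8 = −6.0, subject to the SAP's cap.

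**Step 4: size, by simulation.** All inputs are assumptions. Each run compares one follow-up with baseline; ANCOVA stands in for the GEE in A and B.

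- *A.* Side mean 33 kg, between-subject SD 11, visit error SD 2, SD of true change 4, true effect 4.0 kg. With the limit at the 95th/90th/80th/70th percentile of baseline sides, the estimates are 3.70/3.55/3.36/3.07 kg. Shortfall (4.0 − estimate)/4.0 = 7.5/11.3/16.0/23.3%. Newly lost at follow-up: 5–14% on SA-ER, 2–6% on placebo.
- *B.* Strength at 75% of the SAP 10.4 predicted normal (about 34.5 kg women, 52.5 kg men), between-subject SD 7, side deviation SD about 2.8, error SD 2.5, change SD 3, placebo change −1 kg, true effect 3 kg, 40 per arm, 1,500 runs. With limits of 50/45/40/35 kg, the estimates are 2.78/2.61/2.40/2.25 kg. Shortfall (3 − estimate)/3 = 7.3/13.0/20.0/25.0%. Power is 90/84/72/58%, against 92–94% with no limit. Newly both-sided S, active against placebo: 2.7 vs 0.9% (limit 50) up to 10.3 vs 4.5% (limit 35). With no true effect, rejection stays at 4–5%.
- *C.* A further run, true effect 4.0 kg, other inputs also assumed: 3.75 to 3.22 kg, a shortfall of 6.3% to 19.5%.

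Among true gainers newly S on one side, 36–41% are recorded as losses in B and 19–22% in C.

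**Step 5: alternatives.**

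- Change on the side or sides measured at both visits gives 3.83 to 3.43 kg in C (shortfall 4.3% to 14.3%), with fixed or varying tester limits.
- A Tobit model with the limit known gives 3.93 to 4.04 kg in A.
- Setting A was rerun with site limits varying (SD 3–5 kg, assumed). A Tobit model using one pooled limit then gives 4.26 to 4.87 kg, 6.5% to 21.8% too large.
- Scoring S at the limit also attenuates: 2.85/2.59/2.16/1.70 kg in B.

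**The case against.** The SAP knows about the limitation, states it openly, and aims for the most accurate estimate of strength. The rule is also conservative: with no drug effect it acts alike in both arms.

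S may be rare. SAP 10.2 says weakness is the commonest cause of missing dynamometry data, and SAP 3.3 reports significantly weak knee extensors in Phase 2. Three attempts are made and the highest is used (SAP 5.3), so S may require all three to fail, though the SAP does not say so. The largest shortfall in A needs 30% of baseline sides to be unmeasurable already.

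Censoring has its own difficulty. The limit is the strength of whoever holds the device. There are about 15 sites (Protocol synopsis), and staff are kept consistent only where possible (Protocol 7.5), so no common limit exists.

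These points stand, and they rule out stronger readings a reader might infer:

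- A follow-up S does not remove the subject. The GEE uses Weeks 8 to 48, and the analysis set needs only a baseline and one later value. What is lost is that visit's value, including at Week 48, where the groups are compared. The single-follow-up simulations therefore treat a lost visit as a lost subject.
- A one-sided S is not always scored as a loss; that needs d > 2g.
- The LEC is not affected. Section 10.2 mentions the composites under S, but SAP 5.3 excludes the knee extensors from the LEC.

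They do not rescue the rule. A value known to be high is still scored as absent or as the other side, and no planned analysis would show the consequence.

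**Conclusion.** The concern holds as a scoring defect confined to one key secondary endpoint. Under SAP 10.2, knee-extensor gains can be deleted at a visit, understated, or, when the baseline side gap exceeds twice the gain, recorded as losses. S at baseline can exclude a subject from the endpoint or create a false gain later. Calling the substituted side the weaker one is an inference, but a natural one, since it was still measurable at that visit.

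If the drug works, the net result is bias toward zero and lower power. A reader might infer a risk of false claims of efficacy; the check under no effect does not support that. Nor do the documents support a firm percentage: the range of roughly 6% to 25% rests wholly on assumed SDs, effects and tester limits, and in the mildest case of B power moves only from 92% to 90%. The mechanism is certain; its size is not. This should be corrected, but it does not threaten the primary analysis.

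**What to change.** In SAP 10.2, with matching text in 5.3 and 7.1, for the knee extensors only:

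1. Do not fill a one-sided S from the other side. Use the change on the side or sides validly measured at both baseline and that visit, with the baseline covariate taken from the same side or sides.
2. Prespecify one sensitivity analysis that treats S as right-censored: a Tobit-type repeated-measures model, or multiple imputation bounded below. Take the bound from the subject's own highest valid force on that side or from a tester- or site-specific limit, never from one limit pooled across sites. Handle S at baseline in the same way. Where the tester changed between visits, the subject's own earlier maximum is an assumed bound, and the SAP should say so.
3. State whether S is recorded only when none of the three attempts gives a valid value.
4. Report S counts by arm and visit, baseline included.

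The cost is SAP wording, one additional model and a small table; the SAP already provides for the S code. The force shown when the tester gave way should not be relied on as a bound, because the documents do not say it is recorded. Same-side change removes only part of the attenuation, and the censored analysis needs a distributional assumption above the limit. The current rule can be shown alongside for comparison.

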### 10.3 Computation Formula for Derived HHD Variables

**Individual Muscle Strength Average Score** = (left-side measurement + right-side measurement) / 2

**UE Composite Score** = sum( Individual Muscle Strength Average Score for muscle group gross grip, shoulder abductors, elbow flexors and elbow extensors)

**LE Composite Score** = sum(Individual Muscle Strength Average Score for muscle group hip flexors, hip extensors, hip adductors and knee flexors)

**Total Composite Score** = sum(UE score + LE score)

**Predicted Normal for Individual Muscle Strength Average Score** = (left-side predicted normal + right-side predicted normal) / 2

**Predicted Normal for UE Composite Score** = sum(Predicted Normal for Individual Muscle Strength Average Score for muscle group gross grip, shoulder abductors, elbow flexors and elbow extensors)

**Predicted Normal for LE Composite Score** = sum(Predicted Normal for Individual Muscle Strength Average Score for muscle group hip flexors, hip extensors, hip adductors and knee flexors)

**Predicted Normal for Total Composite Score** = sum(Predicted Normal for UE + Predicted Normal for LE)

**% of predicted normal HHD values** = (Observed strength value/ Predicted normal strength value) \*100%.

Predicted Normal HHD Values can be derived using the regression equations outlined in Appendix 10.4.

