### 5.3 Muscle Strength

The highest value of the three measurements collected for each muscle will be used for all HHD endpoints.

- **HHD Individual Muscle Strength Average Score** is calculated as the average of the right and left raw measurements in kg for an individual muscle group: individual muscle strength raw score = (left-side measurement + right-side measurement) / 2. If a value from the right or left side of an individual muscle group is missing, the missing value will be imputed using the non-missing value from the other side.
- **HHD Upper Extremity (UE) Composite Score** is calculated as the sum of the individual muscle strength average scores for the following muscle groups: gross grip, shoulder abductors, elbow flexors and elbow extensors. If a component individual muscle strength raw score is missing, the composite score will not be computed.
- **HHD Lower Extremity (LE) Composite Score** is calculated as the sum of the individual muscle strength average scores for the following muscle groups: hip flexors, hip extensors, hip abductors, hip adductors and knee flexors. Knee extensors will not be included in the calculation of the LE HHD composite score. If a component individual muscle strength raw score is missing, the composite score will not be computed.
- **HHD Total Composite Score** is calculated as the sum of the HHD UE composite score and the HHD LE composite score. If the UE or LE composite scores are missing, the HHD Total Composite Score will not be computed.
- **Predicted Normal HHD Values** will be derived for the raw right/left strength values from bilateral pinch, gross grip, shoulder abductors, elbow flexors, elbow extensors, hip flexors, hip extensors, hip abductors, hip adductors, knee flexors and knee extensors collected at Baseline using the regression equations outlined in Appendix 10.4. Predicted normal HHD scores for derived variables such as individual muscle raw score, UE/LE composite score, and total composite score will use the same computation method for raw

scores as described above but replace the observed values with the predicted normal HHD values.

- **% of Predicted Normal HHD Values** for the individual muscle groups and composite scores will be calculated as follows: (Observed Value / Predicted Normal HHD Value) \*100%. Baseline predicted normal values will be used to derive % of predicted normal values for all post-baseline study time points.

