### 8.8.1 Analyses of Key Secondary Endpoints

Key secondary endpoints include the following:

- Lower Extremity Composite Score: Muscle strength based on MVIC against a dynamometer will be measured bilaterally in the following lower extremity muscle groups: knee flexors, hip flexors, hip extensors, hip abductors and hip adductors. The LEC is derived from the sum of the average of the right and left raw scores (measured in kg) at each time point through week 48.

- Muscle strength in the knee extensors: bilateral total force (in kg)
- GNEM Functional Activities Scale Mobility Domain score: this is a domain of the GNEM Functional Activities Scale reflective of lower extremity muscle strength

The LEC and Knee extensors will be analyzed in a similar fashion as the primary endpoint including sensitivity analyses as defined in Section 8.1.

Hochberg adjustment for multiplicity (Hochberg 1988) will be used for these three key secondary endpoints.

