### **Hochberg Method for Three Secondary Endpoints**

	p-value	Signif.	p-value	Signif.	p-value	Signif.	p-value	Signif.
Key Secondary Endpoint(1)	≤0.05	Y	>0.05	N	>0.05	N	>0.05	N
Key Secondary Endpoint(2)		Y	≤0.025	Y	>0.025	N	>0.025	N
Key Secondary Endpoint(3)		Y		Y	≤0.0167	Y	>0.0167	N

Key Secondary Endpoints are ranked by p-values from highest to lowest (1 to 2 to 3)

Two sets of analyses will be conducted on the GNEM Functional Activities Scale of Mobility score: one will be on the primary analysis set, and the other will be on the subset of subjects that excludes those subjects with the maximum score at baseline. For example, subjects with score of 40 will be excluded from the analysis of the mobility scale. The same method of analysis model (GEE) as the one for the analysis of the primary endpoints will be used.

In addition, in the subjects with a baseline score less than the maximum of 40, the proportion of subjects in each treatment group who achieve the MID as defined by an increase in Mobility domain score of at least 3.07 points indicating an improvement in mobility or a decrease of at least 3.07 points (GNEM-FAS Dossier) indicating a decline in mobility or changes between -3.07 and 3.07 will also be summarized descriptively as a supportive analysis.

In addition, the cumulative distribution Curve based on change from baseline to Week 48 in FAS mobility will be provided separately in each treatment group.

Analysis of the key secondary endpoints will be repeated in the Per Protocol population.

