### Hand-Held Dynamometry

#### Shoulder abduction and hip abduction

Regression Equations and Multiple Correlations of Sex, Age, and Weight with Muscle Strength

Muscle Action	Side	Equation*	R	R 
Shoulder Abduction	Nondominant	$165.16 - 74.9S - .910A + .126W$	.843	.710
	Dominant	$178.90 - 77.1S - 1.128A + .134W$	.843	.710
Hip Abduction	Nondominant	$203.32 - 73.3S - 1.247A + .192W$	.794	.630
	Dominant	$195.24 - 62.4S - 1.184A + .198W$	.764	.584

(Bohannon 1997b)

\*Muscle strength results in Newtons (N). S, sex (male=0, female=1); A, age (years); W, weight (Newtons).

**Note:** Age and weight values collected at the Baseline visit will be used for the calculation of predicted values for shoulder abduction and hip abduction for all study time points.

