## 10.7 Summary of Efficacy Endpoint and Analysis

Test / Instrument	Endpoint	Type of analysis	Time points for Assessment	Statistical approach at week 48/ET analysis
Physical therapy – Hand-held Dynamometry (HHD)	The changes from baseline in Upper Extremity Composite (UEC) Score over time based on bilateral strength recorded in the following muscle groups: gross grip, shoulder abductors, elbow flexors, and elbow extensors	Primary analysis	Weeks 8, 16, 24, 32, 40, and 48	GEE Model
GNEM Functional Activities Scale (GNEM-FAS)	Changes in muscle strength on mobility domain score (reflective of the lower extremities)	Key secondary efficacy analysis	Weeks 8, 16, 24, 32, 40, and 48	GEE Model
Physical therapy – Hand-held Dynamometry (HHD)	The change from baseline in Lower Extremity Composite (LEC) Score over time based on bilateral strength recorded in the following muscle groups: knee flexors, hip flexors, hip extensors, hip abductors and hip adductors.	Key secondary efficacy analysis	Weeks 8, 16, 24, 32, 40, and 48	GEE Model
	Changes in muscle strength in knee extensor over time based on bilateral total force (kg)			
GNEM Functional Activities Scale (GNEM-FAS)	Changes in muscle strength on upper extremity domain score (reflective of the upper extremities)	Other secondary efficacy analysis	Weeks 8, 16, 24, 32, 40, and 48	GEE Model
Sit to Stand	Changes from baseline on the number of times the subject can rise from a seated to a standing position in a 30-second period will be recorded.	Other secondary efficacy analysis	Weeks 8, 16, 24, 32, 40, and 48	GEE Model
Weighed Arm Lift Test	Changes from baseline on the number of times the subject can raise a 1 kg weight above the head in a 30-second period will be recorded.	Other secondary efficacy analysis	Weeks 8, 16, 24, 32, 40, and 48	GEE Model

Test / Instrument	Endpoint	Type of analysis	Time points for Assessment	Statistical approach at week 48/ET analysis
6-Minute Walk Test	Change from baseline in distance walked (meters) during a six minute period.	Other secondary efficacy analysis	Weeks 8, 16, 24, 32, 40, and 48	GEE Model
	Change from baseline in percent predicted of the distance walked (meters) during a six minute period.			

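### SAP Appendix 10.3 leaves hip abductors out of both lower-extremity composite formulas, contradicting the five-group key secondary LEC defined everywhere else

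*SAP*

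**What the plan says.** Appendix 10.3 gives the LE Composite Score as "sum(Individual Muscle Strength Average Score for muscle group hip flexors, hip extensors, hip adductors and knee flexors". The line for the predicted normal LE composite repeats the same four groups. The Total Composite Score and its predicted normal are built from these two lines.

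SAP 5.3 defines the same composite with five groups: "sum of the individual muscle strength average scores for the following muscle groups: hip flexors, hip extensors, hip abductors, hip adductors and knee flexors". It names one exclusion only: "Knee extensors will not be included in the calculation of the LE HHD composite score". It also states that the composite is not computed when a component is missing.

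SAP 8.8.1, which governs the key secondary analysis, lists "knee flexors, hip flexors, hip extensors, hip abductors and hip adductors. The LEC is derived from the sum". The endpoint table in SAP 10.7 has the "following muscle groups: knee flexors, hip flexors, hip extensors, hip abductors and hip adductors". SAP 4.2 agrees, as do the protocol synopsis and protocol 7.5.2.1.2 and 7.6.4.2.1.

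SAP section 1 gives the SAP precedence over the protocol on analysis methods. It does not say which part of the SAP prevails when two parts disagree.

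**The concern.** The SAP holds two definitions of one multiplicity-controlled endpoint. The appendix version is the one headed as the computation formula, so a programmer could reasonably code from it.

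The two versions differ in two ways:

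- **Value.** The Appendix 10.3 score drops one of five components at every visit, so the change from baseline entering the GEE model differs too.
- **Missingness.** Suppose a subject's hip abductors are untested on both sides because of pain or injury. Under 5.3 and Appendix 10.2 that subject has no LEC at the visit; under 10.3 as printed, the score is kept.

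A different LEC p-value could change the order of the three key secondary p-values and the step at which the Hochberg procedure stops. If the discrepancy were found only after unblinding, the choice of version would be open to challenge.

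**Working it through.** **Step 1: count the groups at each place.**

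| Place | Groups | Hip abductors |
|---|---|---|
| Protocol synopsis, 7.5.2.1.2, 7.6.4.2.1 | 5 | yes |
| SAP 4.2 | 5 | yes |
| SAP 5.3 | 5 | yes |
| SAP 8.8.1 | 5 | yes |
| SAP 10.7 | 5 | yes |
| SAP 10.3, LE Composite Score | 4 | no |
| SAP 10.3, predicted normal LE composite | 4 | no |

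Percent-predicted LEC is a mean over five group averages in protocol 7.5.2.1.2 and SAP 4.4. Appendix 10.4 supplies hip abduction equations and says: "Age and weight values collected at the Baseline visit will be used for the calculation of predicted values for shoulder abduction and hip abduction". Nothing gives a reason to drop the group.

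**Step 2: size of the omitted component.** The plan states no figure to reproduce. For scale, I applied the Appendix 10.4 equations as printed, averaged the two sides, and divided newtons by 9.80665 to get kg. Body sizes are assumptions.

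Hip abductors, man aged 35, 78 kg (weight 764.9 N):
- non-dominant: 203.32 − 1.247×35 + 0.192×764.9 = 306.5 N
- dominant: 195.24 − 1.184×35 + 0.198×764.9 = 305.3 N
- mean 305.9 N, which is 31.2 kg

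Hip abductors, woman aged 35, 62 kg (weight 608.0 N):
- non-dominant: 203.32 − 73.3 − 1.247×35 + 0.192×608.0 = 203.1 N
- dominant: 195.24 − 62.4 − 1.184×35 + 0.198×608.0 = 211.8 N
- mean 207.4 N, which is 21.2 kg

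| Predicted normal (kg) | Man, 35 y, 78 kg, 1.75 m | Woman, 35 y, 62 kg, 1.62 m |
|---|---|---|
| Hip flexors | 57.8 | 37.7 |
| Hip extensors | 45.1 | 29.7 |
| Hip adductors | 32.0 | 22.3 |
| Knee flexors | 27.0 | 18.6 |
| Four groups (10.3) | 161.8 | 108.3 |
| Hip abductors | 31.2 | 21.2 |
| Five groups (5.3) | 193.0 | 129.5 |
| Hip abductor share | 31.2/193.0 = 16.2% | 21.2/129.5 = 16.3% |
| Five-group over four-group | 1.193 | 1.195 |

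Totals come from unrounded components.

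Over eligible ages 18 to 55 and assumed sizes (men 55–110 kg, 1.65–1.85 m; women 45–95 kg, 1.52–1.72 m), the share is 14.5% to 18.7% in men and 14.3% to 20.3% in women. The five-to-four ratio is 1.167 to 1.255 overall.

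**Step 3: which missing data matter.** Weakness does not void the composite under either version. For a muscle too weak to register, Appendix 10.2 says: "In those cases, the value is imputed to 0, and preserves the ability to calculate the UEC and LEC scores". A one-sided gap for any other reason is filled from the other side. Missingness therefore differs only when hip abductors are missing on both sides for a reason other than weakness.

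**Step 4: effect on Hochberg.** The SAP 8.8.1 table states: "Key Secondary Endpoints are ranked by p-values from highest to lowest". The thresholds 0.05, 0.025 and 0.0167 attach to rank, so they do not change. Only the LEC p-value, its rank and the step reached can.

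**Step 5: percent-predicted LEC.** Dividing a five-group observed sum by the four-group predicted normal would inflate percent predicted by 19% to 20% in the two examples and by 17% to 26% over the grid. There is no such inflation if 10.3 is used for both parts, or if percentages are averaged over five groups as in 4.4.

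**The case against.** The strongest reply is that the plan already settles the endpoint. Section 5.3 is the operative definition: it lists five groups, names the only exclusion and gives the missing-component rule. Sections 4.2, 8.8.1 and 10.7 agree, and no body section cites 10.3. Harm requires a programmer to follow one uncited appendix against four concordant listings. This stands as a reason to treat the point as an inexpensive correction rather than a design flaw. It does not remove the contradiction, because no written rule makes the body prevail over an appendix.

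The percent-predicted inflation needs a mixed derivation, and 5.3 says predicted composites are computed in the same way as raw ones. That is correct. The endpoint is also tertiary, and 8.8.3 limits it to summary statistics (although 10.7 lists a GEE model). The inflation range should carry no weight in judging importance.

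The shares describe healthy people at assumed sizes, whereas the trial tests change from baseline in patients with uneven weakness. This also stands. In addition, the women's figures use the printed hip adduction slopes of 0.30 (left) and 0.00 (right), which look uneven. Had the left slope been 0.03 (an assumption), the woman's share would be 16.7% rather than 16.3%, so the scale hardly moves.

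The missingness example is narrow, and SAP 7.1 expects such bilateral gaps to be limited. That is accepted; the difference in value remains.

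**Conclusion.** The concern holds. Both LE lines in Appendix 10.3 contradict the five-group LEC given in every other listing, and the missing group is hip abductors each time. A drafting slip copied from one line to the next is the likely explanation; that is an inference, since the documents do not state the cause.

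This should be fixed because a stated formula for a Hochberg-tested endpoint gives a different endpoint if followed. The omitted component is about 16% of the healthy-normal composite in the two worked examples and 14.3% to 20.3% over the assumed grid. Those figures rest on the Appendix 10.4 equations as printed and on assumed body sizes, and they are not estimates of bias. The documents give no observed hip abductor strength in this disease, so neither the size nor the direction of any effect on the treatment comparison can be derived. The primary UEC endpoint and the Hochberg thresholds are unaffected.

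**What to change.** In Appendix 10.3, add hip abductors to the LE Composite Score line and to the predicted normal LE composite line, so that both match SAP 4.2, 5.3, 8.8.1 and 10.7. The two total composite lines then need no edit, because they are built from the corrected ones. Before unblinding, check the LEC derivation program against 5.3.

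No new missing-data rule is needed; 5.3 and Appendix 10.2 already cover the fifth group. The cost is two words in each of two lines and one program check, with no change to design, data collection or sample size.
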